### **Statistical analyses:**

#### Simulation Study

In preparation of this application we conducted a Monte Carlo simulation study to assess the relative merits of the proposed DTL adaptive design over a non-adaptive, parallel-group approach. Specifically, the goal of this study was to demonstrate that the DTL design would result in the maximum number of subjects being treated in the most promising conditions, i.e., appropriate "pruning" of less effective conditions. Simulation scenarios including one that posits no effect across conditions and others, assuming specific anticipated effects, permits evaluation of Type I and Type II Error rates respectively. Sample size for each simulated trial was set at  $n = 160$ . Response to treatment was defined, dichotomously, as  $> 50\%$  decrease in depression score as measured on the MADRS. Specification of effects for the simulations assumed that the rate of response in the placebo condition is 25%, while 1000 mg aspirin qd and 1000 mg NAC bid have comparable effects with response rates of 50% each. The combination of 1000 mg aspirin qd and 1000 mg NAC bid is anticipated to demonstrate an additive effect yielding a 70% response rate. At 50% information gathering, defined as  $n = 80$  subjects having completed the study, a Bayesian interim analysis determined the posterior probability that treatment conferred benefit. Benefit was defined as the absolute difference in response rate for each treatment relative to placebo. The remaining 80 subjects were allocated to the retained (non-pruned) treatments, with the probability of assignment to any given group based on the number of groups continuing in the study.

Pruning/Retention Rules. Simulation scenarios considered a variety of pruning rules that varied in stringency for 1) detecting a clinically decisive difference ( $>10\%$  from placebo), and 2) selecting the best performing treatment. All simulations assumed a  $\sim\text{Beta}(1,1)$  prior distribution for the probability of treatment response in all study conditions. A  $\text{Beta}(1,1)$  prior models values within the range  $[0,1]$  in which all values have the same probability of occurring. This constitutes a vague, neutral prior distribution which reflects uncertainty preceding data accrual. At 50% of data gathering ( $n = 80$ ) the prior (i.e.  $\sim\text{Beta}(1,1)$ ) was updated with data generated from a binomial distribution for each

condition. The posterior distributions of the differences between each treatment and placebo formed the basis of pruning decisions. A decisive difference is defined as occurring if the posterior probability of there being a <10% difference between any of the treatments and placebo was  $< 0.20$ . Another way of saying this is that if there was a >80% chance that the all treatment-placebo differences were <10% then the simulation concluded that the trial had failed to find a decisive difference. If this first rule identified the existence of a decisive difference for any of the treatments, the algorithm then selected the treatment that had the highest posterior probability of conferring benefit (i.e. the  $p(\text{treatment-control} > 0|\text{data})$  for participants. If the algorithm failed to identify a decisive treatment difference, the 1000 mg aspirin condition was retained as the active treatment. This was done to further our established programmatic goal of evaluating the anti-inflammatory effects of aspirin on depression by providing the most precise effect size estimate possible.

Study performance in terms of maximizing patients allocated to the best-performing conditions and for Type I and Type II Error rates are reported for the design under these retention/pruning criteria.

Simulation of Pruning/Retention Rules. Simulation evaluated the pruning rules for three scenarios. Scenario 1 simulated clinical trials with binomial probabilities of response of 0.25, 0.50, 0.50, and 0.70 for placebo, aspirin, NAC and aspirin + NAC respectively. Scenario 2 addressed the situation in which the effect sizes are less optimistic. Scenario 2 posited binomial probabilities of response of 0.25, 0.30, 0.30, and 0.50 for placebo, aspirin, NAC and aspirin + NAC respectively. Scenario 3 simulated clinical trials with binomial probabilities of response of 0.25, 0.25, 0.25 and 0.25 for placebo, aspirin, NAC and aspirin + NAC respectively. Since this last scenario simulates data in which there is no effect, the probability of identifying a decisive effect is an estimate of the Type I Error Rate for the pruning algorithm.

Simulation of Operating Characteristics. Although Bayesian statistical approaches offer a more efficient means by which to weigh evidence, it is still essential to estimate the probability of making specific types of errors using the current design. We first evaluated, over the course of  $k = 200$  simulated trials with the anticipated effects, how often the design fails to find the posited effect. This yields the equivalent of the Type II Error Rate, with one minus this value corresponding to the power of the design. For Scenario 1,  $k=200$  simulated clinical trials indicated that the probability of identifying a decisive difference was >99%. Including trials for which the algorithm failed to identify a decisive difference as Type II Errors, the selection of the best performing treatment based on the highest posterior probability of benefit identified the combination 82.5% of the time. For Scenario 2,  $k=200$  simulations suggested that the probability of identifying a decisive difference was 98.5%. Counting trials for which the algorithm failed to identify a decisive difference as Type II Errors the selection of the best performing treatment based on the highest posterior probability of benefit identified the aspirin + NAC combination 83% of the time. This corresponds to 84.5% power. Since Scenario 3 simulates data in which there is no effect, the probability of identifying a decisive effect is an estimate if the Type I Error Rate for the pruning algorithm. This final scenario identified a decisive effect in >0.5% of simulated trials. This corresponds to a Type I Error Rate of 0.005.

If  $N = 160$  participants are randomized across four conditions in a 1:1:1:1 ratio, contrasts for treatment response rates versus placebo will use  $n = 40$  participants per cell. For Scenario 1, assuming  $n = 40$  per group and  $\alpha = 0.05$ , power to detect the difference between the proportions 0.25 and 0.50 is 65%. Using the same assumptions power to detect the difference between the proportions 0.25 and 0.70 is >99%. For Scenario 2, assuming  $n = 40$  per group and  $\alpha = 0.05$ , power to detect the difference between 0.25 and 0.5 is 65%. More generally, for comparison of two independent proportions, sample sizes of  $n = 40$  per group and  $\alpha = 0.05$  provide 80% power to detect a difference between 0.25 and 0.55. Such a sample is underpowered for two of the effects in Scenario 1, and all of the effects in Scenario 2. Recall, however that the proposed Bayesian adaptive design results in altered cell sizes such that the most promising treatment and placebo each receive an average of  $n = 60$  participants. (This is substantiated by the simulation results). Assuming  $n = 60$  participants per group and  $\alpha = 0.05$ , power to detect the difference between 0.25 and 0.50 is 81.80%, while power to detect the difference between 0.25 and 0.70 is > 99%. More generally, a sample of this size provide 80% power to detect the difference between 0.25 and 0.49 with  $\alpha = 0.05$ .

In summary, a Bayesian adaptive approach demonstrates adequate operating characteristics (Type I and II Error Rates) for the current trial. The method results in allocation of more participants to the most effective condition. Finally, the approach permits frequent analyses with more desirable Type I and Type II Error rates.

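### The simulation results give two incompatible power figures for Scenario 2 (83% and 84.5%), and a null-scenario result above 0.5% that is equated with a Type I rate of 0.005

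*Combined protocol and SAP*

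**What the plan says.** The relevant text is the paragraph headed Simulation of Operating Characteristics, in the Simulation Study part of Statistical analyses.

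- **Number of runs.** The failure rate was evaluated "over the course of $k = 200$ simulated trials with the anticipated effects".
- **Definition of power.** Of the proportion of runs that miss the posited effect, the plan says: "This yields the equivalent of the Type II Error Rate, with one minus this value corresponding to the power of the design".
- **Scenario 2, first step.** The "simulations suggested that the probability of identifying a decisive difference was 98.5" per cent.
- **Scenario 2, scoring.** The selection result is given "Counting trials for which the algorithm failed to identify a decisive difference as Type II Errors".
- **Scenario 2, result.** On that scoring the highest-posterior rule "identified the aspirin + NAC combination 83% of the time. This corresponds to 84.5% power".
- **Scenario 3 (no effect in any arm).** "This final scenario identified a decisive effect in >0.5% of simulated trials", which the plan then equates with a Type I error rate of 0.005.

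The preceding paragraph on pruning rules adds that when no decisive difference is found, the aspirin-alone arm is the one carried forward.

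**The concern.** The 84.5% is offered as a restatement of the 83% in the sentence before it. Under the paragraph's own definition the two should be the same number, because failures are already included in the 83%. Both describe the same set of simulated trials, so simulation noise cannot explain the difference. The Scenario 3 sentence has a similar fault: a proportion strictly above 0.5% is not a rate of 0.005.

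These are the plan's only simulated error rates. The Simulation Study summary judges the design's Type I and Type II error rates satisfactory, and General Data Analytic Strategies points back to the simulations for the same reassurance. A reader should be able to take each figure at face value, and at present cannot tell which Scenario 2 power or which Scenario 3 result was observed.

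**Working it through.** **Inputs, all from the Simulation of Operating Characteristics paragraph**

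- Simulated trials per scenario: k = 200
- Scenario 2, decisive difference found: 98.5%
- Scenario 2, combination selected, with non-decisive trials scored as errors: 83%
- Scenario 2, stated power: 84.5%
- Power = 1 − Type II error rate

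**Step 1. Convert to counts.**

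- Decisive: 0.985 × 200 = 197, so 200 − 197 = 3 trials were not decisive.
- Combination selected: 0.83 × 200 = 166.
- Stated power: 0.845 × 200 = 169.

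**Step 2. Apply the plan's definition.**

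- Type II errors: 200 − 166 = 34, made up of 3 non-decisive trials and 31 decisive trials that selected another arm.
- Type II error rate: 34/200 = 17.0%.
- Power: 1 − 0.17 = 83.0%.

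**Step 3. Try to reproduce 84.5%.**

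| Route | Calculation | Result |
|---|---|---|
| Plan's definition | 166/200 | 83.0% |
| Conditional on a decisive difference | 166/197 | 84.3% |
| Selection rate times decisive rate | 0.83 × 0.985 | 81.8% |
| Non-decisive trials added as successes | (166 + 3)/200 | 84.5% |

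Of these routes, only the last matches. It contradicts the stated scoring. It also contradicts the retention rule: in those 3 trials aspirin alone is carried forward, so the combination was not selected. Rounding does not help. If 83% stood for 165 or 167 trials, adding 3 would give 168/200 = 84.0% or 170/200 = 85.0%, and dividing by 197 would give 83.8% or 84.8%.

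**Step 4. Compare with Scenario 1.** There, too, non-decisive trials are counted as Type II errors. The result is left at 82.5% (165/200), with no second, higher power figure.

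**Step 5. Scenario 3.** A rate of 0.005 at k = 200 is exactly 1 trial. The text supports three counts, depending on which part is misprinted:

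| Reading | Count | Exact 95% interval |
|---|---|---|
| More than 0.5%, read literally | at least 2/200 (1.0%) | 0.12–3.57% for 2/200 |
| Exactly 0.5% | 1/200 | 0.01–2.75% |
| Less than 0.5%, if the sign is reversed | 0/200 | 0–1.83% |

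The plan states none of these counts.

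**Step 6. Scale of the simulation error.** For 83% at k = 200 the standard error is √(0.83 × 0.17/200) = 2.7 points, and the exact 95% interval is 77.1–87.9%.

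**The case against.** The strongest reply is that this changes nothing. The gap is 1.5 points, smaller than the 2.7-point simulation standard error, and the interval around 83% contains 84.5%. Both values exceed 80%, and 83% is no worse than the 82.5% that the plan reports for Scenario 1. The 84.5% appears only once. The argument for adequate power in the next paragraph rests on a separate calculation with 60 participants per group (81.80% for 0.25 against 0.50). All of this stands, and it is why the point is minor. It does not remove the contradiction, because both figures describe the same 200 runs.

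A second reply is that the documents do not show which figure is wrong. That also stands. The match of 166 + 3 with 169 is suggestive, but a slip in typing either number fits the text as well. The 83% has the better claim only because it is the figure tied explicitly to the stated scoring.

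Third, the sign in the Scenario 3 sentence may be a typing or PDF-reading error. If so, correcting the sign or giving the count settles it.

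A reader might go further and infer that the design is underpowered, or that the true Type I error is several times 0.005. The documents do not support either inference from these sentences. The first would need a power figure below the target, and 83% is not. The second would rest on the upper limit of an interval for a count that the plan never gives.

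**Conclusion.** The contradiction is real and its effect is small. By the paragraph's own definition and scoring, Scenario 2 power is 83% (166/200) with Type II error 17%, not 84.5% with 15.5%. If 83% is the correct count, power is overstated by 1.5 points. That condition cannot be checked from the documents, and the add-back of 3 trials is the likely explanation, not an established one. Separately, a Scenario 3 result above 0.5% and a Type I rate of 0.005 cannot both hold as written. The discrepancy does not touch the sample size, the pruning rule or the separate calculation with 60 per group. This is a reporting correction of minor severity.

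**What to change.** 1. Check the Scenario 2 output. Restate power as 83% and Type II error as 17%, unless the output shows that 83% is the misprint; in that case correct the 83% and make the two sentences agree.
2. In the Scenario 3 sentence, replace the inequality with the observed number of trials out of 200, and give the Type I rate that follows from it.
3. Optional: add simulation intervals to the reported rates (for 83% at k = 200, 77.1–87.9%), or rerun with more trials. At 10,000 trials the standard error would be √(0.83 × 0.17/10,000) = 0.4 points. This is good practice but is not needed to remove the contradiction.

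Items 1 and 2 cost a look at the stored output and edits to two sentences. If the output has not been kept, the scenarios would have to be rerun to settle the counts. No change to the design follows.

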represented by a prior distribution, with observed data, represented by the likelihood. This yields a posterior distribution from which statements about the probability of a given effect size can be made. As treatment outcomes accumulate over the course of the trial, posterior probabilities are used to estimate treatment effects and inform the pruning of less effective treatments based on a priori decision rules.

Designing an adaptive trial typically begins with a simulation study to address issues such as timing and frequency of interim analyses, and to understand the operating characteristics associated with the criteria for dropping conditions [57]. In keeping with the proposed DTL design, a Monte Carlo simulation study was conducted (see Statistical Analyses) to assess the relative merits of this design over a non-adaptive parallel-group approach. Simulation results, support the proposed DTL design in showing that under scenarios reflecting the hypothesized treatment effects, the adaptive design allocates more subjects to the more promising treatment conditions, i.e., appropriate “pruning” of less effective conditions. Using simulated data, the design performs well as demonstrated by adequate power and Type I error rates. Thus, employing the proposed DTL design is likely to yield the same conclusions as the classical fixed (non-adaptive) design, but with greater statistical precision for the most promising treatments.

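### The interim decisive-difference rule is worded in two ways that disagree, and no single rule can give the reported 98.5% detection in Scenario 2 together with a Type I error of 0.005

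*Combined protocol and SAP*

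**What the plan says.** Under *Pruning/Retention Rules* (Simulation Study), the prior is Beta(1,1) in every arm and the interim takes place when 80 of 160 subjects have completed. A decisive difference exists if "the posterior probability of there being a <10% difference between any of the treatments and placebo was" below 0.20. The next sentence presents itself as the same rule in other words: "if there was a >80% chance that the all treatment-placebo differences were <10% then the simulation concluded that the trial had failed". If the rule is met, the arm with the highest posterior probability of beating placebo goes forward. If not, there is a default: "If the algorithm failed to identify a decisive treatment difference, the 1000 mg aspirin condition was retained as the active treatment".

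*Simulation of Operating Characteristics* then reports 200 simulated trials per scenario:

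- Scenario 1 (response rates 0.25, 0.50, 0.50, 0.70): decisive in more than 99%, combination selected in 82.5%.
- Scenario 2 (0.25, 0.30, 0.30, 0.50): "simulations suggested that the probability of identifying a decisive difference was 98.5" per cent. The rule "identified the aspirin + NAC combination 83% of the time", with non-decisive trials already counted as Type II errors. The text continues: "This corresponds to 84.5% power".
- Scenario 3 (0.25 in all arms): "This final scenario identified a decisive effect in >0.5% of simulated trials. This corresponds to a Type I Error Rate of 0.005".

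The plan relies on these results. *Need for efficient drug development studies* says that "the design performs well as demonstrated by adequate power and Type I error rates". The summary that closes the Simulation Study calls the operating characteristics adequate, and *General Data Analytic Strategies* says the error rates are at appropriate levels.

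**The concern.** The two sentences set different thresholds. If the posterior probability of a small difference is, say, 0.50, the first sentence says not decisive and the second says decisive. A statistician running the interim could not tell which to apply. The answer determines whether the best-looking arm or, by default, aspirin receives the second-half patients.

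The reported figures do not settle it. Detection of 98.5% in Scenario 2, where only one arm differs materially from placebo, points to a very permissive rule. A null rate of 0.5% points to a very strict one. With about 20 patients per arm, both from one rule is implausible on its face. If one figure is wrong, the error rates that the plan cites as evidence for the design are wrong too.

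**Working it through.** **Inputs.** Interim at n = 80, Beta(1,1) priors, the 10-point margin, the 0.20 and 0.80 thresholds, the selection rule and the three sets of response rates all come from the Simulation Study. Twenty per arm is an assumption: 80/4, using the 1:1:1:1 ratio that the section gives for the fixed design. No other first-stage ratio is given.

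**Formulas.** With x_i responders of 20 in arm i, θ_i | x_i ~ Beta(1 + x_i, 21 − x_i). Let d_j = θ_j − θ_placebo, q_j = P(d_j < 0.10 | data) and Q = P(all three d_j < 0.10 | data).

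- Sentence 1: decisive if some q_j < 0.20 (any arm), or if Q < 0.20 (joint). A stricter reading requires every arm to pass.
- Sentence 2: decisive unless Q > 0.80 (joint), or unless every q_j > 0.80 (arm by arm).

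Each rate is the exact sum of binomial probabilities over all 21⁴ interim outcomes. Ties for the best arm are split at random.

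**One outcome as illustration.** Suppose every arm has 5 of 20 responders, so no difference is observed. Each posterior is Beta(6, 16), with variance 6 × 16 / (22² × 23) = 0.00862. The SD of a difference is √(2 × 0.00862) = 0.131, so q_j ≈ Φ(0.10/0.131) ≈ 0.78. That is above 0.20, so sentence 1 (any arm) says not decisive. It is also below 0.80, so sentence 2 (arm by arm) says decisive, although the arms are identical.

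**Probability of a decisive finding**

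| Rule | Scenario 1 | Scenario 2 | Scenario 3 (null) |
|---|---|---|---|
| Plan, as reported | >99% | 98.5% | 0.5% |
| Sentence 1, any arm | 96.1% | 60.4% | 12.4% |
| Sentence 1, joint | 97.7% | 66.8% | 20.3% |
| Sentence 1, every arm separately | 39.3% | 2.7% | 0.35% |
| Sentence 1, every arm jointly | 29.9% | 1.6% | 0.13% |
| Sentence 2, joint | >99.9% | 98.9% | 86.4% |
| Sentence 2, arm by arm | >99.9% | 98.1% | 80.6% |

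**Decisive and combination selected (Scenarios 1 and 2).** The plan reports 82.5% and 83%. Sentence 2 gives 83.6% and 82.5–83.0%. Sentence 1 gives 80.9% and 53.8% (any arm), or 81.8% and 57.8% (joint).

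Sentence 2 therefore reproduces the plan's Scenario 1 and 2 figures and misses only the null figure. The readings that come near the null figure detect Scenario 2 in under 3% of trials.

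**Bound for any rule.** The placebo count has the same distribution in Scenarios 2 and 3. The best possible rule therefore orders outcomes by the likelihood ratio of the three active-arm counts.

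- At size 0.005, detection in Scenario 2 is at most 47.5%.
- Detection of 98.5% needs a size of at least 40.3%.

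**Simulation error.** With 200 trials, 1/200 has an exact 95% interval of 0.01%–2.75%, and 197/200 has 95.7%–99.7%. At size 2.75% the bound is 71.8%, far below 95.7%. At 40 per arm, twice the stated interim, the bound is 82.7% at size 0.005 and 94.2% at 2.75%, still below 95.7%.

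**Consequences of the wording**

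| | Sentence 1 (any arm; joint) | Sentence 2 (both readings) |
|---|---|---|
| Aspirin retained, null | 92%; 86% | 42–46% |
| Aspirin retained, Scenario 2 | 43%; 38% | 9–10% |
| Combination selected, Scenario 2 | 54%; 58% | about 83% |
| Final test rejects, Scenario 2 | about 54%; 58% | 74% |

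The last row uses 400,000 simulated trials, with the retained arm and placebo topped up to 60 each and a two-sided 0.05 chi-square test. Under the null that test rejects in about 6% of trials under either sentence.

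**Two smaller slips in the same paragraph.** Non-decisive trials are counted as errors, which gives 83%, yet power is then given as 84.5%. The gap equals the 1.5% of non-decisive trials (83 + 1.5 = 84.5), though the text shows no derivation. A rate described as above 0.5% is also equated with 0.005.

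**The case against.** The strongest reply is that this is one misreported figure in a design justification. Sentence 2 matches every other simulated result to within about 1 point, so it is probably the rule that was run. Its 81–86% null rate also sounds worse than it is. The design always carries one active arm forward, so under the null a false decisive finding only determines which of three equally ineffective arms gets more patients, and the final test still rejects in about 6% of trials. The section also says that a variety of pruning rules was considered, and 20 per arm is inferred.

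Much of this stands. The 81–86% is not a rate of false efficacy claims, and sentence 2 may well be the rule simulated. The stated reason for making no multiplicity adjustment is the likelihood principle, which this point does not touch.

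It does not remove the problem. The plan says its results are reported under the criteria just described, and no stringency gives both figures. Even 40 per arm does not reconcile them. A bound that assumes 60 in the combination arm would (98.7% at size 2.75%), but the stated n = 80 interim at equal allocation gives no such arm. Most importantly, the written plan still holds two rules that lead to different arms being retained.

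**Conclusion.** The concern holds. The two sentences are not equivalent; this follows from the text alone. On 20 per arm (assumed), 98.5% detection in Scenario 2 and a null rate of 0.005 cannot come from one rule: the most that size 0.005 allows is 47.5%, and simulation error with 200 trials does not close the gap. Taken as the simulated rule, sentence 2 has an interim false-decisive rate of 81–86%, more than 160 times the reported figure. The practical effect is on selection: in Scenario 2 the correct arm goes forward in 54–58% of trials under sentence 1 (any arm or joint) and about 83% under sentence 2. The statements that the error rates are adequate have no support as written. The finding concerns the interim pruning step; it does not show an inflated error in the final comparison beyond the roughly 6% noted above.

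**What to change.** 1. State one decisive-difference rule as a formula, giving the threshold and whether it applies per arm or jointly, and delete the other wording.
2. The sponsor chooses the rule knowing the trade-off. Sentence 1 (any arm) has an interim false-decisive rate of about 12% but about 54% correct selection in Scenario 2. Sentence 2 has about 83% correct selection but a false-decisive rate of 81–86%.
3. State the number per arm at the interim and rerun all three scenarios under the chosen rule. Use clearly more than 200 trials; 10,000 or more is a reasonable number, though not essential to the point.
4. Restate the decisive, correct-selection and null rates, labelled as properties of the pruning rule, and report the final test's error separately.
5. Make the power figure follow the stated Type II definition, and resolve the conflict between above 0.5% and 0.005.
6. Revise the claims of adequate or appropriate error rates in *Need for efficient drug development studies*, the Simulation Study summary and *General Data Analytic Strategies* to fit the new results.

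The rerun and rewording take little time. The choice of rule is a real design decision: moving from sentence 2 to sentence 1 (any arm) lowers final-test rejection in Scenario 2 from 74% to about 54%. Under either choice the reported figures become less favourable.

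### The interim rule is worded in two non-equivalent ways, the stated 0.005 Type I error does not belong to the rule behind the stated power, and the final test's operating characteristics are not reported

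*Combined protocol and SAP*

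**What the plan says.** All of this is in the combined protocol and SAP, mainly under Statistical analyses, Simulation Study.

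- **Decisive rule (Pruning/Retention Rules).** A difference is decisive if "the posterior probability of there being a <10% difference between any of the treatments and placebo was" below 0.20. The next sentence offers a restatement: the trial fails to find a decisive difference if there is more than an 80% chance that all differences are under 10%. If decisive, the arm with the highest posterior probability of beating placebo is kept; otherwise aspirin is kept.
- **Decisive rates (Simulation of Operating Characteristics, 200 trials per scenario).** Scenario 1: above 99%, combination selected 82.5%. Scenario 2: "the probability of identifying a decisive difference was 98.5" percent, combination selected 83%, then described as 84.5% power. Scenario 3 (null): printed as greater than 0.5% and called "an estimate if the Type I Error Rate for the pruning algorithm". "This corresponds to a Type I Error Rate of 0.005".
- **Power (same section).** On 40 per group: "Such a sample is underpowered for two of the effects in Scenario 1, and all of the effects in Scenario 2". The answer offered is that "the most promising treatment and placebo each receive an average of" 60 participants, and that at this size "power to detect the difference between 0.25 and 0.50 is 81.80" percent.
- **Conclusion.** "a Bayesian adaptive approach demonstrates adequate operating characteristics (Type I and II Error Rates) for the current trial".
- **Final analysis (General Data Analytic Strategies).** A beta-binomial model and a chi-square test. The section says that frequentist interim looks need adjustment, exempts Bayesian analyses, and relies on the simulation for acceptable error rates.

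**The concern.** The reader is given a very small Type I error, selection probabilities above 80% and a power of 81.80%, and is told that together they show the design works. These describe different things: the interim pruning step, the choice of an arm, and a fixed two-group comparison. None is the probability that the trial ends with a correct, or a false, significant result.

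The 0.005 should also come from the same rule as the other decisive rates. If it does not, the simulation does not support the statement on error rates. The interim decision would also be open to two interpretations when real data arrive, and these differ greatly in how often they keep the combination.

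Finally, Aims I and II concern aspirin alone and NAC alone. A reader who carries 81.80% over to them could take a non-significant result for a dropped arm as evidence of no effect.

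**Working it through.** **Inputs.** Response rates for placebo/aspirin/NAC/combination: Scenario 1 0.25/0.50/0.50/0.70; Scenario 2 0.25/0.30/0.30/0.50; Scenario 3 0.25 throughout. Beta(1,1) priors. Interim at 80 patients, so 20 per arm at 1:1:1:1; then 40 more each to the retained arm and placebo. Final test: uncorrected chi-square at 1.96. One response per patient under the first assigned arm.

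**1. The plan's own power figures.** Sum Bin(x; n, 0.25) × Bin(y; n, 0.50) over all (x, y) with |z| > 1.96, where z = (y/n − x/n) / √(p̄(1 − p̄)·2/n) and p̄ = (x + y)/(2n).
- n=40: 64.7% (stated 65%).
- n=60: 81.80% (stated 81.80%).

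Both reproduce.

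**2. The two wordings differ.** Let P_k be the posterior probability that arm k minus placebo is under 10 points.
- Wording A (the definition): decisive if P_k < 0.20 for some arm.
- Wording B (the restatement, arm by arm): not decisive only if P_k > 0.80 for every arm.

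Example: every arm has 5 of 20 responders. Each posterior is Beta(6,16), with variance 6×16/(22²×23) = 0.00862. The difference has SD √(2×0.00862) = 0.131, so P_k ≈ Φ(0.10/0.131) = 0.78. Under A the trial is not decisive, since 0.78 is not below 0.20. Under B it is decisive, since 0.78 is not above 0.80, although the arms are identical.

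**3. Decisive rates by reading** (400,000 simulated trials per scenario, ties split at random):

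| Reading | Scen. 1 | Scen. 2 | Scen. 3 | Combination kept, Scen. 1 / 2 |
|---|---|---|---|---|
| Stated | >99% | 98.5% | 0.5% | 82.5% / 83% |
| A, any arm | 96% | 60% | 12% | 81% / 54% |
| B, arm by arm | 99.98% | 98.1% | about 80% | 83.6% / 82.5% |
| Every arm must have P_k < 0.20 | 39% | 3% | 0.3% | 31% / 2% |

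Taking B as one joint probability over the three arms gives 98.9% in Scenario 2 and about 86% in Scenario 3. B fits Scenarios 1 and 2, including selection of the combination, but not Scenario 3. Only the every-arm reading comes near 0.005, and it fails Scenarios 1 and 2.

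**4. Simulation noise.** 0.005 × 200 = 1 trial. The exact 95% interval for 1 in 200 is 0.01% to 2.8%, which excludes both 12% and 80%.

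**5. Selection, power and both together (Scenario 2, combination).** The 84.5% does not follow from the 83% beside it. Dividing by the decisive rate gives 0.83/0.985 = 84.3%; adding the non-decisive trials gives 83 + 1.5 = 84.5, but the text does not say that this was done. In either case it is a selection probability.
- From the plan's own figures: 0.83 × 0.818 = 68%.
- Simulated, retained and significant: about 70% under B (0.825 × 0.853 = 70%); about 50% under A (0.539 × 0.931 = 50%).

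**6. Aspirin and NAC in Scenario 1.** Under A or B, aspirin is retained in 8–12% of trials and NAC in about 8%. A dropped arm has about 20 patients. If it were tested against all 60 placebo patients, the exact power for 0.50 (n=20) versus 0.25 (n=60) is 55.7%. Averaged over all trials the simulation gives 56–57%.

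**7. Final test under the 25% null, retained arm versus placebo (A or B).** About 6.3% two-sided, against 5.2% for a fixed 60/60 pair. False superiority is 3.7% (A) to 4.8% (B), against a nominal 2.5%.

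**The case against.** The strongest reply is that much of this is a declared trade-off. The plan ties n=60 to the most promising arm and placebo, and the section on efficient drug development says that precision is gained for promising arms by dropping others. On that view 81.80% belongs to the combination in Scenario 2, where it is not too high: power given retention is 85% under Wording B. This stands. A reader might infer that 81.80% is miscalculated, or is claimed for aspirin and NAC. It reproduces exactly, and nowhere is it stated as the power of those arms in Scenario 1. The fault is its placement, directly after the remark that two Scenario 1 effects are underpowered.

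It is also fair that the plan never says dropped arms will be formally tested, so 56% describes a hypothetical test. Against concurrent placebo patients only, the figure averaged over trials would be 39–41%.

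A reader might also infer that the trial has only 50% power. That figure needs Wording A, whose Scenario 2 rates (60% decisive, 54% combination) contradict the reported results. It matters only if Wording A governs the real interim.

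Nor does the 80% in Scenario 3 mean that 80% of null trials would claim efficacy. It is the interim decisive rate, and a significant final test is still needed. The excess at that test is modest for a phase II screen with a parallel Bayesian analysis.

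None of this explains why the three decisive rates cannot come from one rule, or supplies the missing joint power and final-test error.

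**Conclusion.** The point holds for the rule and the reporting. The two wordings are not equivalent, and no reading tried gives >99%, 98.5% and 0.5% together. The 0.005 therefore does not belong to the rule behind the stated selection rates, and 200 trials cannot explain the gap. The stated 84.5% power is a selection probability, and 81.80% is power given retention. For the Scenario 2 combination, retained and significant is about 70% on the reading that fits the reported results. For aspirin and NAC in Scenario 1, 81.80% does not apply; a test against all placebo patients would have about 56%, below the 65% already called underpowered. The final chi-square has about 6.3% two-sided error at a 25% null, a small but unreported excess.

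These figures assume exactly 20 per arm at the interim, one retained arm, no dropout adjustment and no effect of the week-8 re-randomisation of non-responders. If two active arms continued and the last 80 patients were split equally over three groups, each would reach about 20 + 80/3 ≈ 47, not 60, and the power figures would change. The documents do not support the stronger conclusions that the design is invalid or that one particular critical value is required.

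**What to change.** 1. Choose one wording of the decisive rule, and state whether one arm or several continue. The section on efficient drug development and the Simulation Study's allocation text allow several; Pruning/Retention Rules selects one.
2. Re-run the simulation through the final test, with many more than 200 trials and with re-randomised patients counted as the analysis will count them.
3. Replace 0.005 (and the greater-than sign printed with 0.5%) and the 84.5% with the corrected figures.
4. Label each power figure by aim and scenario as given retained or as retained and significant, and report the Type I error of the final chi-square.
5. State that 81.80% does not apply to dropped arms. Report those arms as estimates with intervals unless a formal test is specified.
6. If the final-test error is judged too high, set the threshold from that simulation. I do not propose a fixed value: under the assumptions above, z = 2.25 would lower the Scenario 2 retained-and-significant probability from 70–71% to 64% (Wording B), and the right value depends on the unmodelled re-randomisation.

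Cost: programming time and SAP text, with no extra patients. The stated power and error figures will look less favourable.
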